6. REPORTING ADVERSE EVENTS

6.1 Adverse Events (AE's)

An adverse event is any undesirable clinical occurrence in a patient whether it is considered to be drug related or not. The observed or volunteered adverse events regardless of suspected causal relationship to the study treatment will be recorded on the adverse event page of the eCRF. An adverse event is classified by the investigator as mild (1), moderate (2), severe (3) life threatening (4) or death (5) according to the National Cancer Institute Common Terminology Criteria for Adverse Events v4.0 (CTCAE, Appendix 2).

Events involving adverse treatment reactions, illness with onset during the study, or exacerbations of pre-existing illness should be recorded. Objective test finding (e.g. laboratory results) that need treatment should also be recorded.

Note that the following examples of adverse events do not need to be recorded:

- Medical or surgical procedures (e.g. endoscopy, appendectomy); the condition that leads to the procedure is an AE.
- Hospitalisation for elective treatment of a pre-existing condition (known/diagnosed prior to informed consent signature) that did not worsen from baseline.
- Situations where an untoward medical occurrence did not occur (e.g. social and/or convenience admission to a hospital, admission for routine examination).
- Anticipated day-to-day fluctuations of pre-existing disease(s) or condition(s) present or detected at the start of the study that do not worsen.
- The disease/disorder being studied, or expected relapse, progression, signs, or symptoms of the disease/disorder being studied, unless more severe than expected for the patient's condition.

An example of events which are to be recorded in the medical history section of the eCRF and not as an AE is eg. pre-existing conditions or signs and/or symptoms present in a patient prior to the start of the study (i.e. prior to the first study product administration).

The investigator should also provide information on the duration (start and stop date), relation to study treatment, start of concomitant therapy and outcome of the adverse event. Follow up of the adverse event after therapy discontinuation, is required if the adverse event or its sequelae persist. Follow up is required until the event or its sequelae resolve or stabilize at a level acceptable to the investigator. Adverse event information will be collected from the start of drug treatment up to the visit 30-35 days after stop of drug treatment or longer if drug related adverse events have not resolved or not returned to baseline, whichever is longest. A representative of the Sponsor shall consider all adverse events and, if required, shall report them to the appropriate authorities.

6.2 Serious Adverse Events (SAE's)

A serious adverse event is any untoward medical occurrence that at any dose:

- results in death
- is life-threatening
- requires inpatient hospitalisation or prolongation of existing hospitalization (except for elective hospitalization for a pre-existing condition that did not worsen from baseline; See 6.1)
- results in persistent or significant disability / incapacity or
- is a congenital anomaly/birth defect.

If, as a result of an adverse event during a clinical investigation, a patient has to be hospitalised, or their hospitalisation is unduly prolonged because of potential disability or danger to life or because an intervention has been necessitated or the event is terminal, the adverse event is regarded as serious. For example, if – according to the investigator - an adverse event causes foetal distress, foetal death or a congenital anomaly or malignancy results from the use of the drug during a clinical investigation, this would be processed as a serious adverse event.

All serious adverse events which occur from the start of study treatment up to the Safety follow up visit 30-35 days after EOT visit whether or not considered related to the treatment, must be reported immediately (within one day of the investigator becoming aware of the adverse event) by sending a completed Serious Adverse Event Report Form by e-mail or fax to EAU RF representatives:

[contact] with a copy to the recipient at EAU RF: [contact]. Serious adverse events **related to either study participation or related to study treatment** should be reported throughout the entire study period.

An event which is part of the natural course of the disease under study (i.e., disease relapse or progression) is captured as an efficacy measure; therefore it does not need to be reported as a SAE. Progression/relapse of the tumor will be recorded in the clinical assessments in the eCRF. Death due to a progressive disease is to be recorded on a specific form in the eCRF but not as a SAE.

However, if relapse or progression of the underlying disease is more severe than what would normally be expected for the patient, or if the investigator considers that there was a causal relationship between study drug treatment or protocol design/procedures and the disease

progression/relapse, then this must be reported as a SAE. Any new cancer (non-related to the cancer under study) must be reported as an SAE.

A representative of the Sponsor will report SAE's to the IRB/IEC that approved the protocol and to the regulatory authorities via the annual general progress report or development safety update reports (DSURs). (See also 8.4)

6.3 Suspected Unexpected Serious Adverse Reactions (SUSAR's)

Suspected unexpected adverse reactions are SAE's considered to be related to study treatment, of which the nature, or severity, is not consistent with the information in the Investigators drug Brochure (IB).

A representative of the Sponsor will report (expedited) all SUSARs to the investigators, competent authorities and IEC's. The expedited reporting will occur within the per law defined time intervals which is currently not later than 15 days after the Sponsor has first knowledge of the adverse reactions. For fatal or life threatening cases the term is currently a maximum of 7 days for a preliminary report, with another 8 days for completion of the report.

7. STATISTICAL CONSIDERATIONS

7.1 Patient Accrual, Study Duration and Calculation of Patient Numbers

The recruitment period will be 2 years and patients will be followed for an additional 2 years or until relapse or progression. 2-Year relapse-free survival (RFS) rate is the primary endpoint. No interim analyses are planned. Patients will be consecutively molecularly screened and enrolled into the study. It is expected that about 35% of the total screened patients will be eligible and will be enrolled in this study to receive Pemigatinib treatment. Treatment will be continued for a maximum period of 12 months or until the evidence of disease relapse or unacceptable toxicity development. The assumption is that treatment with Pemigatinib will result in a significant higher 2-year RFS rate at 2 years of 45% RFS compared to the reported 30% RFS at 2 years in bladder cancer patients [3].

Statistical Power Calculations:

In an exact single-stage phase II design [24] with power: 0.80; one-sided alpha: 0.10; H0: 2-year RFS: 30%; H1: 2-year RFS: 45% and follow-up duration of 2 years, the total number of eligible and treated patients needed to be enrolled is 50. Patients who withdraw from the study before completing the study period of 2 years, cannot be included in the calculation of the 2-year RFS rate. We estimate that ~15% of the patients will be withdrawn. Therefore, we need a total of 56 patients enrolled. Cut-off to reject the alternative hypothesis H1 is a total of 20 or more patients who experience relapse or progression at or before 2 years of study follow up.

A total of 56 patients needed in this phase II trial is corresponding to approximately 150 patients needed for molecular pre-screening. The primary analysis includes the planned analysis of the primary endpoint 2-year RFS rate which will be analyzed at the 2-years follow-up time point. RFS is defined as the time from the date of start of treatment until disease relapse or progression by investigator determination, or death due to any cause, whichever occurs first. See also 4.4.3.

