A radiological assessment of disease status will be performed at screening (after radical surgery). Subsequently, disease status will be assessed according to daily urological practice until the start of new anticancer therapy, disease relapse, death or end of study. Follow-up imaging scans are usually based on the recurrence possibility (timing, probability, site, and potential treatment) and functional aspects. In spite of low level of evidence, a suggested oncologic follow-up schedule includes CT scans every 4 months during the first year and every 6 months until the third year [22]. During the investigators meeting at the occasion of the annual EAU meeting in Barcelona, on March 17th, 2019, the investigators proposed and agreed to use a 12 weeks interval (+/- 1 week) for imaging procedures in this high risk group of patients. Relapse free survival will be assessed starting from date of first dose and then every 12 weeks until disease relapse or death. Final assessment of the 2-year relapse free survival rate will be done at 2 years. Overall survival will be assessed from the first dose until death (every 12 weeks from disease relapse to death or termination of the study). (See Appendix 6)

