7.2 Efficacy Analysis Population

The intention to treat (ITT) population will serve as the population for the primary and key secondary efficacy analyses. For the secondary efficacy analyses, all enrolled and eligible patients who will receive at least one dose of the study drug will be included.

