7.4.2 Relapse Free Survival Analysis and 2 year RFS rate

Relapse free survival is defined as the time from the date of start of study treatment until disease relapse or progression by Investigator determination, or death due to any cause, whichever occurs first. Relapse free survival will be analyzed and graphically presented by the Kaplan-Meier method. The percentage of patients with relapse free survival at 2 years will be calculated with its 95% Confidence Interval.

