7.4.3 Overall Survival Analysis

Overall Survival (OS) is defined as the time from the date of start of study treatment to death due to any cause. Participants without documented death at the time of analysis will be censored at the date of the last follow-up. Overall survival will be analyzed and graphically presented by the Kaplan-Meier method. The percentage of patients who survive at 2 years will be calculated with its 95% Confidence Interval.

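### Section 7.1 removes patients who withdraw before 2 years from the primary 2-year RFS rate, Section 7.2 makes ITT the primary population, and RFS has no named 2-year estimator and no censoring rule

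*Combined protocol and SAP*

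**What the plan says.** Four parts of the plan bear on one number, the 2-year RFS rate.

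- **Section 7.1**, under the power calculation: "Patients who withdraw from the study before completing the study period of 2 years, cannot be included in the calculation" of that rate. About 15% are expected to withdraw, and 50 evaluable patients become 56 enrolled.
- **Section 7.2**: "The intention to treat (ITT) population will serve as the population for the primary and key secondary efficacy analyses". ITT is spelled out in the abbreviation list but not defined further.
- **Section 7.4.2**: RFS is analysed and plotted by Kaplan-Meier. A separate sentence adds: "The percentage of patients with relapse free survival at 2 years will be calculated with its 95% Confidence Interval". It names neither estimator nor denominator.
- **Section 7.4.3**, for overall survival only: "Participants without documented death at the time of analysis will be censored at the date of the last follow-up". RFS has no counterpart.

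Section 4 has disease status assessed "until the start of new anticancer therapy, disease relapse, death or end of study". Sections 4.1.5 and 4.1.6 likewise end disease follow-up when new therapy starts. None of them says whether that is an RFS event, a censoring or an exclusion. The statement in 7.4.1 that missing data are not replaced belongs to demographics, safety and biomarkers.

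**The concern.** A set that leaves out patients because they withdrew is not an intention-to-treat set, so 7.1 and 7.2 give different denominators for the same primary result. Since 7.4.2 does not settle the matter, two analysts could each follow the plan and report different primary estimates. In a single-arm trial there is no comparator in which a denominator effect could partly cancel: the estimate is set directly against a fixed 30%. If the choice is made after the data are seen, the result is open to challenge whichever way it falls.

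**Working it through.** **Inputs (7.1).** Null rate 30%, alternative 45%, one-sided alpha 0.10, power 0.80, 50 evaluable, 56 enrolled, about 15% withdrawal. The documents give no withdrawal timing, so everything on timing below is an assumption.

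**1. The plan's own figure.** The smallest exact single-stage design has n = 50 and needs 20 relapse-free patients: P(X ≥ 20 | 50, 0.30) = 0.085 and P(X ≥ 20 | 50, 0.45) = 0.803. The 50 reproduces. The 56 corresponds to a loss of 6/56 = 10.7%; at 15%, 56 × 0.85 = 47.6 remain. Both loss rates are therefore used.

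**2. What exclusion does to the estimate.** Assume exponential RFS, random withdrawal at a constant hazard, and observed relapses always counted. Write S for the true 2-year RFS and c for the share withdrawing event-free.

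- Relapse hazard: λ = −ln(S)/2, which is 0.602 for S = 0.30 and 0.399 for S = 0.45.
- Withdrawal hazard μ solves μ/(λ+μ) × (1 − exp(−2(λ+μ))) = c. For c = 0.15, μ = 0.144 and 0.121.
- Event-free and still on study at 2 years: F = exp(−2(λ+μ)) = 0.2247 and 0.3535.
- Completers-only rate: F/(1 − c) = 0.2247/0.85 = 26.4% and 0.3535/0.85 = 41.6%.

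The rate falls because patients must be event-free to be dropped. Under the null, (0.30 − 0.2247)/0.15 = 50% of them would have stayed relapse-free, against 30% overall.

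| Withdrawal | True 30% becomes | True 45% becomes |
|---|---|---|
| 5% | 28.9% | 43.9% |
| 10.7% | 27.5% | 42.7% |
| 15% | 26.4% | 41.6% |
| 20% | 25.1% | 40.3% |

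**3. Other patterns at 15%.**

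- Withdrawals only in year 1: 28.3% and 43.4%. Only in the first 3 months: 29.6% and 44.6%.
- Relapsed patients who later withdraw at the same hazard are dropped too: 30.0% and 45.0%. There is no bias, but 25% and 21% of patients are excluded.
- Withdrawal linked to relapse: if a share q of withdrawn patients would have relapsed, the null rate becomes (0.30 − 0.15(1 − q))/0.85. This is 30.0%, 31.8%, 33.5% and 35.3% for q = 70%, 80%, 90% and 100%. The last is a worst-case bound.

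**4. The decision.** Section 7.1 rejects H1 at "20 or more patients who experience relapse or progression at or before 2 years of study follow up". Dropping event-free patients leaves a count of relapses unchanged. That cut-off is itself wrong: step 1 shows that 20 is a count of relapse-free patients, and requiring at most 19 relapses among 50 has power of about 1% at a true 45%. Only with 20 read as relapse-free patients does the bias in step 2 reach the test. With an exact cut-off re-set for each remaining n, averaged over Binomial(56, 1 − c):

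| Withdrawal | Power with bias | Power without | Alpha with bias | Alpha without |
|---|---|---|---|---|
| 10.7% | 66% | 78% | about 3% | 7.2% |
| 15% | 60% | 76% | 2.2% | 7.4% |

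Under linked withdrawal with a cut-off of 20 of 48, the false-positive rate is 5.7%, 9.6%, 14.9% and 21.8% for the four values of q. With 20 of 50 and 10.7% loss it is 8.5%, 11.8%, 15.9% and 20.8%, passing 10% at about q = 75%.

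**The case against.** **The sentence may only explain the step from 50 to 56.** It stands under the power calculation, and the analysis sections contain no exclusion. That may well have been the intent. As worded, though, it names the rate and says who is left out of it, so it reads as an analysis rule.

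**A reader might infer that 7.4.2 also contradicts 7.1 by requiring Kaplan-Meier.** The text does not go that far. Kaplan-Meier is assigned to the RFS analysis and plot, and the sentence on the 2-year percentage names no method. The estimator is unspecified; the contradiction is with 7.2.

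**A reader might infer that the exclusion alters the go/no-go result.** On the printed rule, dropping event-free withdrawals changes nothing, as step 4 shows.

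**A reader might take the downward bias as established.** It depends on counting every observed relapse. Section 7.1 supports that reading in part, since "patients will be followed for an additional 2 years or until relapse or progression". But relapsed patients stay in survival follow-up (4.1.6, 5.4) and could still withdraw before 2 years, so a literal reading drops them too. Timing also matters, as step 3 shows.

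**The scale of withdrawal may be small.** Section 5.4 keeps patients who stop for toxicity in follow-up and encourages others to stay, and 4.4.1 bars other treatment for the bladder cancer during the study. These limit the problem. Section 5.4 still allows removal for non-compliance or at the investigator's discretion, and 4.1.5 and 4.1.6 foresee new therapy before relapse.

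**Conclusion.** The point stands: 7.1 and 7.2 conflict on who enters the primary estimate, the 2-year estimator is unnamed, and RFS has no censoring rule for withdrawal or new anticancer therapy. This should be settled before any analysis.

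Under constant-hazard random withdrawal with observed relapses always counted, the completers-only estimate is low by about 3.5 percentage points at 15% withdrawal (30% to 26.4%, 45% to 41.6%). Across 5% to 20% withdrawal, the shortfall runs from about 1 to 5 points. The bias nearly vanishes if withdrawals are very early. It turns upward if withdrawn patients are clearly more likely to relapse than the 70% expected under the null. Its direction therefore cannot be fixed from the documents. The loss of power, to about 60% from 76% at 15% and to 66% from 78% at 10.7%, is conditional on the separate cut-off error being corrected.

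**What to change.** 1. Delete the exclusion sentence in 7.1, or reword it as a planning allowance only.
2. In 7.1, 7.2 and 7.4.2, define the primary estimate as Kaplan-Meier RFS at 24 months in one population: all enrolled and treated patients, with ITT defined to match.
3. Read the estimate so that it includes the 2-year scan and its window. Section 4 says: "Final assessment of the 2-year relapse free survival rate will be done at 2 years". With 12-weekly scans, stopping at week 96 would estimate about 0.30^(96/104) = 33% and 0.45^(96/104) = 48% in place of 30% and 45%.
4. Censor patients who withdraw or are lost without an event at their last disease assessment.
5. State whether new anticancer therapy before relapse is an RFS event or a censoring, and run the other choice as a sensitivity analysis.
6. Make the decision rule and stated power match the estimator. One option is to reject H0 if the one-sided 90% complementary log-log lower limit exceeds 30%. Simulated with 56 patients, 12-weekly scans and 10.7% to 15% random withdrawal, this gives alpha of about 9% and power of about 80%.
7. Add an analysis counting withdrawals as failures, labelled as a worst-case bound. It should not be a second pass/fail test: with 22 of 56 required, its power is 48% at 10.7% withdrawal and 31% at 15%.

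**Cost.** The patients and visits stay the same, but this changes the primary analysis and the power statement must be rewritten. Under the option in item 6, a large-sample test replaces the exact one. Kaplan-Meier still assumes non-informative censoring, so withdrawal linked to coming relapse would still bias it.

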5. PATIENT SELECTION & WITHDRAWAL CRITERIA

5.1 Study Population

A total of 56 patients with FGFR alterations as assessed by a centralized Foundation Medicine test (Foundation One) will be eligible to start Pemigatinib after providing their informed consent if they meet all of the following inclusion criteria.

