5.4 Patient Withdrawal and Early Dropouts (off study)

In the patient informed consent form the patients will be informed that they have the right to withdraw from the study at any time without affecting their subsequent care and may be withdrawn at the investigator's discretion at any time. In the event that the patient drops out, the investigator will, if possible, indicate the reason for withdrawal. Reasonable effort will be made to contact any patient lost to follow up during the course of the study in order to complete assessments and retrieve any outstanding data. Patients withdrawn from the trial will not be replaced.

Off study criteria:

- When the investigator considers it in the best interest of the patient that he/she will be withdrawn
- Patient or legal representative request withdrawal of informed consent
- Lost to follow up or administrative reasons
- Non-compliance with study treatment or procedure requirements.
- Study termination by ethical- or health authorities or the Sponsor.
- Others, only applicable after consultation with the sponsors study monitor.

Participants who discontinue study treatment prior to completion of the treatment period should be encouraged to continue to be followed for all remaining study visits.

When a participant discontinues/withdraws from participation in the trial, if possible, all applicable activities scheduled for the final study visit should be performed at the time of discontinuation. Any adverse events which are present at the time of discontinuation/withdrawal should be followed in accordance with the safety requirements outlined in chapter 6 - Adverse Events.

If the patient discontinues study treatment and actively withdraws consent for collection of follow-up data (safety follow-up or disease assessment), then no additional data collection should occur; however, patients will have the option of withdrawing consent for study treatment but continuing in the follow-up period of the study for safety/efficacy assessments.

Notes:

- Patients who experience unacceptable study drug related adverse events should stop treatment with the study drug. These patients continue follow up for disease status and survival.

- Patients who develop a relapse or metastases of disease stop study drug treatment and they are asked to consent with biopsy and subsequent genomic sequencing after relapse or metastases, whereafter follow up for survival only is continued.

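### Section 7.1: 50 evaluable patients with about 15% excluded withdrawals needs 59 enrolled, not 56; 56 allows for only 10.7%

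*Combined protocol and SAP*

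**What the plan says.** All the steps are in Section 7.1 of the combined protocol and SAP.

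- Design: "In an exact single-stage phase II design [24] with power: 0.80; one-sided alpha: 0.10", with 2-year RFS of 30% under H0 and 45% under H1.
- Size of the test: "the total number of eligible and treated patients needed to be enrolled is 50".
- Withdrawals: "Patients who withdraw from the study before completing the study period of 2 years, cannot be included in the calculation" of the 2-year RFS rate.
- Enrolment: "We estimate that ~15% of the patients will be withdrawn. Therefore, we need a total of 56 patients enrolled".

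Section 5.4 adds: "Patients withdrawn from the trial will not be replaced". The total of 56 recurs in the Synopsis, in Section 8.10 and in Section 5.1 ("A total of 56 patients with FGFR alterations as assessed by a centralized Foundation Medicine test").

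Two other statements bear on who is counted. Section 7.2 says: "The intention to treat (ITT) population will serve as the population for the primary and key secondary efficacy analyses". Section 7.4.2 analyses RFS by the Kaplan-Meier method and says: "The percentage of patients with relapse free survival at 2 years will be calculated with its 95% Confidence Interval".

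**The concern.** The plan presents 56 as the result of adding a 15% allowance to 50, and it is not that result. If withdrawals are excluded and not replaced, the expected evaluable number falls below the 50 on which the power statement rests.

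There is a second consequence. The plan gives one cut-off number, 20, tied to 50 evaluable patients, and no rule for any other count. Under the plan's own assumptions a count of exactly 50 is unlikely. The cut-off would then have to be chosen after the evaluable number is known, in an open-label single-arm trial where outcomes are visible.

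**Working it through.** **Inputs.** From Section 7.1: p0 = 0.30, p1 = 0.45, one-sided alpha 0.10, power 0.80, 50 patients required, withdrawal about 15%, withdrawals excluded, 56 enrolled. From Section 5.4: no replacement. Cut-offs below count relapse-free patients. Section 7.1 words its 20 as patients who relapse, which is a separate defect.

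**Step 1: the base number.** For each n, take the smallest r with P(X ≥ r | n, 0.30) ≤ 0.10; power is P(X ≥ r | n, 0.45). At n = 50, r = 20: alpha 0.0848, power 0.8026. No smaller n reaches 0.80. The 50 is reproduced, so the fault lies only in the step from 50 to 56.

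**Step 2: the allowance.**

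- Correct form, N/(1 − d): 50/0.85 = 58.8, so 59. Check: 59 × 0.85 = 50.2, while 58 × 0.85 = 49.3 falls short.
- Looser form, N × (1 + d): 50 × 1.15 = 57.5, so 58.
- Rate implied by 56: 1 − 50/56 = 10.7%. A 10% rate gives 50/0.90 = 55.6, so 56.
- Evaluable at 15%: 56 × 0.85 = 47.6.

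Reading the rate loosely does not help: 14% gives 50/0.86 = 58.1 and 12% gives 50/0.88 = 56.8, both above 56.

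**Step 3: power by evaluable number, cut-off re-derived.**

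| Evaluable n | Cut-off r | Alpha | Power |
|---|---|---|---|
| 44 | 18 | 0.0812 | 0.7560 |
| 45 | 18 | 0.0986 | 0.7944 |
| 46 | 19 | 0.0681 | 0.7416 |
| 47 | 19 | 0.0831 | 0.7807 |
| 48 | 20 | 0.0570 | 0.7276 |
| 49 | 20 | 0.0700 | 0.7671 |
| 50 | 20 | 0.0848 | 0.8026 |
| 51 | 21 | 0.0589 | 0.7538 |
| 52 | 21 | 0.0717 | 0.7899 |
| 53 | 21 | 0.0862 | 0.8223 |
| 54 | 22 | 0.0605 | 0.7774 |
| 55 | 22 | 0.0731 | 0.8104 |
| 56 | 22 | 0.0874 | 0.8398 |

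With 20 kept at n = 47, power is 0.684. With 20 kept at n = 51, alpha is 0.1015.

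**Step 4: averaging over the evaluable number.** Assumption, not in the documents: each patient withdraws with probability 0.15, independently of outcome, so the evaluable number is Bin(enrolled, 0.85).

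| Enrolled | Mean power, cut-off re-derived | Mean power, cut-off fixed at 20 |
|---|---|---|
| 56 | 76.4% | 69.8% |
| 59 | 77.7% | 79.3% |
| Difference (unrounded inputs) | 1.3 points | 9.5 points |

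With 56 enrolled, the chance of 47 or fewer evaluable is 46.7%, of 48 to 50 (the only range where 20 is the right cut-off) 39.6%, and of 51 or more 13.6%. The chance of at least 50 is 24.6%, against 60.9% with 59 enrolled.

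**The case against.** The strongest reply is that the effect is small. Three patients separate 56 from 59, the rate is given as approximate, and with a re-derived cut-off the difference is 1.3 points of averaged power. Even 59 averages 77.7%, so most of the gap to 80% comes from the random evaluable number and the discreteness of the binomial. That stands and limits the weight of the point, but the stated derivation is still wrong.

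The 9.5-point figure is open to challenge. With 59 enrolled there is a 46.6% chance of 51 or more evaluable, where a fixed 20 exceeds alpha 0.10, so part of the advantage is bought with type I error. Averaged over the evaluable number, type I error at 59 with 20 fixed is 0.094, still below 0.10. The figure is best read as the price of having only one cut-off.

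A third reply is that the exclusion rule may not govern, because Section 7.2 names the ITT population and Section 7.4.2 uses Kaplan-Meier. If the 2-year percentage is a Kaplan-Meier estimate, withdrawn patients contribute until censoring and the power figures above do not apply. Neither section supplies the missing step from 50 to 56, because Section 7.1 justifies 56 by the exclusion.

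Finally, Sections 4.1.5 and 5.4 keep patients who stop the drug in follow-up, so those not evaluable may be fewer than 15%. That is possible, but Section 7.1 applies the 15% directly to withdrawals it excludes.

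**Conclusion.** The inconsistency is real and does not depend on any assumption about outcomes: 50 evaluable at 15% excluded and unreplaced withdrawal requires 59, and 56 fits only 10.7%. Because 56 is used consistently elsewhere, the wrong figure may be the 15% rather than the 56.

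The stated power of 0.80 is not supported at the plan's own withdrawal rate. It is about 73% to 78% at 48 and 47 evaluable, or 76.4% on average, provided that the exclusion rule governs, withdrawal is independent of outcome and the cut-off is re-derived. Type I error is not inflated at 47 to 49 evaluable. This should be corrected, but it does not undermine the design.

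**What to change.** Keep 56 and amend Section 7.1 in one of two ways.

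- If 15% was the slip, correct the allowance to about 10.7%, with a reason for expecting that rate rather than a fit to 56. Averaged power with a random evaluable number would then be about 77.6%.
- If 15% is the real expectation, keep it and restate the power as about 73% to 78% (76.4% averaged).

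Raising enrolment to 59 would also repair the arithmetic, but for 1.3 points it would change the total throughout the protocol and the pre-screening number.

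In either case, state the cut-off for each possible evaluable number in advance. Counting relapse-free patients at alpha ≤ 0.10, these are 18 for 44–45, 19 for 46–47, 20 for 48–50, 21 for 51–53 and 22 for 54–56. Extend the table downwards, since 43 or fewer has a 6.8% chance at 15% withdrawal (18 at 43; 17 at 40–42).

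The cost is wording and a short table, with no extra patients, visits or data.

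Separately, the exclusion in Section 7.1 must be reconciled with the ITT population in Section 7.2. That is a design decision outside this cost. If all 56 are analysed, the cut-off becomes 22 (alpha 0.087, power 84.0% with complete outcomes); keeping 20 would give alpha 0.213. If 15% withdrew independently of outcome and were counted as failures, a rule the plan does not state, power with 22 would be about 49%.

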4.4.3 Relapse or Progression

All types of relapse will be included i.e. local, regional and distant metastasis as well as second primary tumor of the upper urinary tract. In addition, all deaths occurring without prior documentation of tumor relapse will be considered as an event. Any new primary cancer will not be considered as relapse and should be reported as SAE. All relapses must be documented by radiological evidence or biopsy, as determined by the investigator. Suspicion of relapse based on physical examination findings or laboratory signs must be confirmed by radiological examination

and/or biopsy. Equivocal findings on standard radiological imaging should be confirmed by repeated examinations or cytology/histology or other imaging techniques. The date of relapse or progression as indicated by the date of radiology or biopsy as confirmed by the investigator, will be used as the timepoint of relapse or progression. At disease relapse or progression, a biopsy and subsequent genomic sequencing at the sponsors central laboratory is recommended after written informed consent of the patient.

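### The only decision rule in section 7.1 is inverted: 20 is the number of relapse-free patients needed to reject H0, but the text uses it as the number of relapses that rejects H1

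*Combined protocol and SAP*

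**What the plan says.** Section 7.1 specifies the design: "In an exact single-stage phase II design [24] with power: 0.80; one-sided alpha: 0.10", with "H0: 2-year RFS: 30%; H1: 2-year RFS: 45% and follow-up duration of 2 years". It puts the number of eligible and treated patients at 50 and raises enrolment to 56 to allow for about 15% withdrawal. It then gives one decision rule: "Cut-off to reject the alternative hypothesis H1 is a total of 20 or more patients who experience relapse or progression". The count covers the whole 2-year follow-up. The same section plans no interim analysis.

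Three other statements bear on the rule:

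- **Events.** Section 7.1 defines RFS to include death from any cause, and section 4.4.3 says that "all deaths occurring without prior documentation of tumor relapse will be considered as an event". The cut-off sentence names only relapse or progression.
- **Denominator.** On the 2-year rate, section 7.1 says "Patients who withdraw from the study before completing the study period of 2 years, cannot be included in the calculation". Section 7.2 says "The intention to treat (ITT) population will serve as the population for the primary and key secondary efficacy analyses".
- **Analysis.** Section 7.4.2 plans a Kaplan-Meier curve and states: "The percentage of patients with relapse free survival at 2 years will be calculated with its 95% Confidence Interval". It contains no test and no success criterion.

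**The concern.** The hypotheses are written as proportions relapse-free, but the cut-off counts patients who relapse. A threshold of 20 events in 50 lies below the number expected under either hypothesis, so it cannot separate them. It cannot be an early futility rule either, because no interim look is planned and events are counted over the full 2 years.

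This is the only formal criterion for the primary endpoint. Applied as written, it would normally call a drug that meets its 45% target a failure. If it were put right only after the data were seen, the success criterion of an open-label, single-arm trial would have been chosen post hoc.

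**Working it through.** **Inputs (section 7.1).** p0 = 0.30 and p1 = 0.45 relapse-free at 2 years; one-sided alpha 0.10; power 0.80; n = 50; cut-off 20; 56 enrolled; withdrawal about 15%.

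**1. Reproduce the design.** Let X be the number relapse-free, X ~ Bin(n, p). For each n, take the smallest r with P(X ≥ r | 0.30) ≤ 0.10. Then take the smallest n with P(X ≥ r | 0.45) ≥ 0.80. The result is n = 50, r = 20. At n = 50:

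| r (relapse-free) | alpha | power |
|---|---|---|
| 19 | 0.1406 | 0.873 |
| 20 | 0.0848 | 0.8026 |
| 21 | 0.0478 | 0.714 |

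Only r = 20 meets both limits. The plan's 50 and 20 are therefore this design's sample size and its success count in relapse-free patients.

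**2. Translate the rule into events.** H0 is not rejected when X ≤ 19, that is, when events ≥ 50 − 19 = 31. P(events ≥ 31) is 0.197 at RFS 45% and 0.915 at RFS 30%, the complements of the power and alpha above.

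**3. Evaluate the rule as written, with all RFS events counted.** The event probability is 1 − RFS.

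- Expected events: 50 × 0.55 = 27.5 under H1 and 50 × 0.70 = 35 under H0. Both exceed 20.
- P(events ≥ 20 | n = 50, 0.55) = 0.9884, so power is 1 − 0.9884 = 1.2%.
- P(events ≤ 19 | n = 50, 0.70) = 2.8 × 10⁻⁶, so alpha is about 0.0003%.
- Escaping rejection of H1 takes at least 31 of 50 relapse-free (62%). Even at a true RFS of 60%, H1 is rejected 55% of the time.
- With other denominators, at RFS 45%, H1 is rejected with probability 0.968 (n = 47), 0.977 (n = 48) and 0.9988 (n = 56).

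**4. Literal reading, with deaths without relapse left out.** Let s be the share of RFS events that are such deaths. The documents give no value, so s is an assumption shown as a range. The counted-event probability is (1 − RFS)(1 − s), with n = 50.

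| s | H1 rejected at RFS 45% | power | alpha |
|---|---|---|---|
| 5% | 97.0% | 3.0% | 0.003% |
| 10% | 93.2% | 6.8% | 0.03% |
| 20% | 76.1% | 23.9% | 0.8% |
| 30% | 46.7% | 53.3% | 7.8% |

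Power is below 80% in every row.

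**5. Denominators other than 50.** For each n, the cut-off is the smallest r with P(X ≥ r | 0.30) ≤ 0.10, and power is P(X ≥ r | 0.45). Every patient's 2-year status is taken as known.

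| n | relapse-free needed | alpha | power |
|---|---|---|---|
| 47 | 19 | 0.083 | 0.781 |
| 48 | 20 | 0.057 | 0.728 |
| 49 | 20 | 0.070 | 0.767 |
| 50 | 20 | 0.085 | 0.803 |
| 51 | 21 | 0.059 | 0.754 |
| 52 | 21 | 0.072 | 0.790 |
| 53 | 21 | 0.086 | 0.822 |
| 54 | 22 | 0.061 | 0.777 |
| 55 | 22 | 0.073 | 0.810 |
| 56 | 22 | 0.087 | 0.840 |

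Holding 20 fixed would give alpha 0.141 at n = 53 and 0.213 at n = 56. The plan's own withdrawal figure leaves 56 × 0.85 = 47.6 patients evaluated.

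**The case against.** The inversion and its figures are not in dispute. The case on the other side is about weight and scope.

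- **Limited harm.** The Kaplan-Meier estimate and its interval do not depend on the cut-off, and no visit, dose or safety rule hangs on it. This stands, and it confines the damage to the formal test conclusion. That conclusion is still the only stated criterion for the primary endpoint.
- **Deaths.** Naming only relapse or progression is most naturally shorthand, since section 7.1 goes on to define RFS with death included and section 4.4.3 agrees. This is fair. The 98.8% figure belongs to that reading, and the range in step 4 only shows that the literal reading does not rescue the rule. At a 30% share, H1 would be rejected slightly less than half the time, so the near-certain rejection holds only if all RFS events count.
- **Denominator.** The conflict between sections 7.1 and 7.2 is a separate issue, and the inversion holds whichever applies. True, but a count rule cannot be applied without a denominator, so both belong in one edit.
- **Gaps in a simple correction.** A rule fixed at 50 would probably not be the one used if about 47.6 are evaluated, and more withdrawals could take n below 47 (at n = 46 the cut-off is 19, alpha 0.068, power 0.742). At 20 of 50 the exact 95% interval is 26.4% to 54.8%, which includes 30%; its lower limit first exceeds 30% at 23 of 50. These points stand and are taken up in the fix.

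**Conclusion.** The concern holds. Section 7.1 gives the right number for its design but attaches it to the wrong outcome and the wrong hypothesis, and no other section corrects it. At n = 50, with all RFS events counted, the written rule rejects H1 98.8% of the time when the 45% target is true. Its power is 1.2% against the stated 80%, and its alpha is about 0.0003% against the stated 10%. The intended rule has alpha 8.5% and power 80.3%.

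These figures assume a known 2-year status for every patient in the denominator and a binomial count. Confidence is high, because the stated inputs reproduce both the 50 and the 20 exactly. This must be corrected before the primary analysis.

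**What to change.** Replace the cut-off sentence in section 7.1 with:

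> H0 is rejected if at least 20 of 50 patients in the primary analysis set are alive and relapse-free at 2 years; equivalently, H0 is not rejected if 31 or more of 50 have relapse, progression or death at or before 2 years.

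In the same edit:

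1. Name the primary denominator, reconciling the exclusion of withdrawn patients in section 7.1 with ITT in section 7.2, and say how patients with unknown 2-year status are counted.
2. Add the table of cut-offs by denominator from step 5, with the rule that generates them, so that a denominator outside 47 to 56 is also covered. Do not carry 20 forward as a fixed count above 50.
3. Say whether the one-sided 0.10 rule or the 95% interval in section 7.4.2 governs the conclusion.

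The cost is a few sentences and a ten-row table. Correcting the rule needs no extra patients or procedures. It does not by itself secure 80% power: power is below 0.80 at 47, 48, 49, 51, 52 and 54 patients, and at the 47 or 48 implied by the plan's own withdrawal figure it is 0.78 or 0.73.
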